18.2. Sample collection for further translational studies

All trial participants will be asked if they are willing to donate a baseline blood sample to be collected and stored for use in further translational sub-studies within the FAST-Forward Boost trial. The objectives of these studies will be defined separately. Participation in this aspect of the trial will be optional and subject to patients' written informed consent. For patients who are also participating in the early side effects translational sub-study, the baseline blood sample will count as the first of the three blood samples described in section 18.1 above.

The blood samples will be sent by the site to the ICR laboratory, where they will be stored until the end of the trial. Consent will also be sought to allow these samples to be used for future research projects, subject to ethical approval.

Subject to patients' written informed consent, archival tissue samples (FFPE blocks) of primary tumour at the time of diagnosis or any other applicable surgical procedures (including subsequent disease relapses or new primary cancers) and associated information, including imaging scans obtained as part of standard care, may be requested for translational sub-studies as part of FAST-Forward Boost, which will be defined separately. Consent will also be sought to allow these samples to be used for future research projects, ethics approval permitting.

Subject to patients' written informed consent, other samples taken as part of previous or future routine care (such as but not limited to blood, scans, urine) may be requested for translational studies as part of FAST-Forward Boost which will be defined separately. Consent will also be sought to allow these samples to be used for future research projects, ethics approval permitting.

All tissue/other samples will remain at site of collection until relevant translational projects are approved and funded. The TMG will review and approve any sample data access request.

NCI CTCAE	National Cancer Institute Common Terminology Criteria for Adverse Events
NHS	National Health Service
NIHR-HTA	National Institute for Health and Care Research Health Technology Assessment
PI	Principal Investigator
PIS	Patient Information Sheet
PPI	Patient and Public Involvement
PRO	Patient Reported Outcomes
QoL	Quality of Life
R&D	Research and Development
RCT	Randomised controlled Trial
RT	Radiotherapy
RTOG	Radiation Therapy Oncology Group
RTTQA	National Radiotherapy Trials Quality Assurance
SAE	Serious Adverse Event
SAR	Serious Adverse Reaction
SIB	Simultaneous Integrated Boost
SUSAR	Suspected Unexpected Serious Adverse Reaction
SWAT	Study within a Trial
TMG	Trial Management Group
TSC	Trial Steering Committee

A2. PATIENT REPORTED OUTCOMES

Rationale for PRO measurement

Patient reported outcomes (PROs) have become an important measure in breast cancer research. This is an umbrella term coined for any subjective report from the patients on outcomes such as quality of life, functional well-being and satisfaction of treatment received. There is evidence that radiotherapy causes long-term effects on quality of life in terms of altered breast appearance, breast, arm, and shoulder symptoms, as well as a possible impact on some general aspects of health, such as fatigue. In evaluating radiotherapy interventions, it is important that these effects are understood from the patients' perspective. All participants must be asked to consent to complete PRO assessments, but this will be non-mandatory for participants in the main study.

FAST-Forward Boost aims to evaluate acute and late effects of 1-week SIB radiotherapy compared with the standard 3-week SIB. PRO evaluations in FAST-Forward Boost are based on standard instruments used in previous studies in this setting that will provide interpretable data and allow comparison with other relevant trials. The scales selected include specific measures for evaluating breast cancer therapies, body image, post-radiotherapy symptoms, fatigue and psychological distress together with a general cancer health-related quality of life scale and a generic quality of life scale widely used in health economic evaluations. These measures have been used in the START, IMPORT, FAST-Forward and PARABLE breast radiotherapy trials. Assessments will be carried out over at least 5 years of follow-up. Timings of assessments are in line or similar to those used in these previous breast radiotherapy trials.

Measures used for all participants

- EORTC QLQ-C30 is a 30-item cancer quality of life-specific instrument, which comprises 5 functional sub-scales, 2 symptom subscales and additional symptom items and questions about global health and global quality of life.(61)
- EORTC QLQ-BR23 breast cancer module is a 23-item scale designed for use in breast cancer patients. It incorporates five multi-item scales to assess systemic therapy side effects, breast symptoms, arm symptoms, body image and sexual functioning. In addition, single items assess sexual enjoyment, hair loss and future perspective.(62)
- 10-item Body Image Scale (BIS) (of which 4 items are already incorporated in the BR23) was designed for use with cancer patients and has been widely used in national breast cancer treatment trials. (63)
- EORTC QLQ FA12 is a 12-item scale on fatigue which will be used in this trial to provide detailed data to assess the short- and longer-term impact of radiotherapy.(64)
- Protocol-specific items to assess radiotherapy symptoms as used in previous breast radiotherapy trials: 13 items specific to post-radiotherapy breast symptoms and shoulder/arm functioning. These include change in skin appearance, change in overall appearance of the breast, breast shrinkage and hardening, position of the nipple, difficulty getting a bra to fit, shoulder stiffness, experience of pins and needles in arm, numbness on fingers, weakness on arms or hands.

Please refer to appendix A3 for details of additional questionnaires that will be used to inform health economics analysis.

Measures used in the early side effects sub-study

In addition, the first 115 patients recruited into each arm of the trial will take part in the early side-effects sub-study and will complete the following questionnaires:

- PRO-CTCAE v5.0 items relating to acute toxicities in skin, breast, and oesophagus
- Trial specific questions: 4-items specific to any acute symptoms in the treated breast: skin reddening, skin blistering, breast swelling and breast pain or tenderness during and immediately after radiotherapy.
- Hospital Anxiety and Depression Scale (HADS)(65) will measure psychological distress. HADS has been widely used in clinical trials to date and provides clinically interpretable outcomes. This is not a trial endpoint itself but will be assessed pre-treatment and used to support interpretation of the other patient-reported outcome data.

PRO-CTCAE and trial specific questions on acute symptom data will be collected pre-treatment and at weeks 1-7 and 12 from the start of radiotherapy. Patients in the sub-study will also complete the QLQ FA12 at an additional time point.

There are separate versions of the paper PRO booklets until the 3 month timepoint, ones which contain the early side-effects sub-study additional questionnaires and those that do not.

Electronic PRO booklets will be automatically sent to the patient at the relevant timepoints.

A3. HEALTH ECONOMICS

Rationale for HE measurement

The primary outcome measure for the health economic (HE) evaluation will be the cost per quality-adjusted life year (QALY) gained. This will be estimated from health resource usage and duration of time spent in different health states, with health status measured by EQ-5D-5L. The objective of the health economic evaluation is to establish whether a 5-fraction radiotherapy boost to the breast (test groups 1 and 2) is cost effective relative to current UK practice (15-fraction radiotherapy boost, control) and in comparison, to other NHS activity. The analysis will also have broader implications for cost-effectiveness of the approach when delivered in other countries.

The health economic analysis will make use of a generic, preference-based measure of HRQoL (health-related quality of life). The objective is to have an index measure of HRQoL where quality of life and absence of morbidity are valued on the same scale as quantity or length of life. This enables the calculation of quality adjusted survival where duration of time spent experiencing certain health states (e.g. receiving radiotherapy, experiencing a local recurrence) is weighted according to the HRQoL value associated with that health state.(66, 67)

Health care resource use data (UK only)

The aim of this part of the HE evaluation is to compare the treatment groups in terms of Health care resource use. This primarily relates to the cost of resources used to provide each radiotherapy regimen and the cost of treating adverse events (short and long term) and further breast cancer events. For example, the trial will collect any information on hospitalisations associated with adverse events and/or further breast cancer events. Questions relating to resource use, such as the use of specialist nurses, GP visits, and outpatient visits for treating adverse events from treatment will be incorporated in the PRO questionnaires, as was done successfully in the FAST-Forward and IMPORT LOW trials. Information on the resource use associated with recurrent breast cancer events will be obtained from literature review and published NHS costs.

Quality of life measure

The **EQ-5D-5L** is a standardised instrument designed for self-completion in an adult population.(68) questionnaire asks patients to describe their current health status by specifying one of five levels of severity (no problems, slight problems, moderate problems, severe problems and unable to/extreme problems) across five dimensions (mobility, self-care, usual activities, pain/discomfort, anxiety/depression). We will follow National Institute for Health and Clinical Excellence(NICE) recommendations to estimate QALYs from EQ-5D-5L so that our results are comparable with other appraisals undertaken to inform NHS treatment decisions.(69, 70)

The resultant quality of life scores will be compared across time and between 5-fraction radiotherapy boost (test groups 1 and 2) and 15-fraction radiotherapy boost (control). This analysis will inform the health economic analysis in calculating quality adjusted survival for patients receiving each regimen. To extrapolate beyond the trial these data will be supplemented by a literature search of previous studies of the health-related quality of life impact of treatment and events in patients with breast cancer.

The EQ-5D-5L will enable the calculation of quality adjusted life years that would be consistent and comparable with those routinely used in the economic evaluation of health care technologies by the NICE in the UK.(71)

Out of pocket costs (UK only)

Radiotherapy treatment can have important impacts on personal income through lost earnings and costs associated with travelling to receive therapy. These will be captured using a questionnaire administered during periods patients are on treatment. This information will be used to supplement the analysis based from the NHS and personal social services (PSS) perspective.

Timing of assessments

Where participants have consented to PRO participation, EQ-5D-5L will be collected at: pre-treatment, week 1, week 2, week 3, month 3, year 1, year 3 and year 5 from treatment start date. The “Health care resource use questionnaire” (UK only) will be collected at: month 3, year 1, year 3 and year 5 post treatment start date. The “out of pocket costs” questionnaire (UK only) will be collected during the on treatment period i.e. week 1, week 2 and week 3.

Methods

A decision analytic model describing a series of health states and health events experienced by patients with early breast cancer will be developed.(72). This will be based on the model developed to undertake cost-effectiveness analysis of radiotherapy regimens studied in the FAST-Forward and IMPORT LOW trials .(37) This model will be used to synthesise information from the trial and other published studies in order to estimate costs and quality adjusted survival over an appropriate time horizon from the perspective of the UK NHS and PSS. Uncertainty around the values used in the decision analytic model will be characterised using probabilistic sensitivity analysis. The trial regimens will be evaluated using standard cost-effectiveness analysis. Data from the two test groups will be combined and compared with the control group consistent with previous HE analyses in FAST-Forward. If one strategy is not found to be dominant (i.e. less costly and more effective) in comparison to the other, then an incremental cost-effectiveness ratio (ICER) will be determined. (73) The ICER will be based on the mean costs and mean QALYs estimated within the probabilistic sensitivity analysis of the decision model. Uncertainty around cost-effectiveness will be described using cost-effectiveness acceptability curves which describe the probability that an intervention is cost-effective.

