in 1-week using a SIB technique. However, level 1 evidence is required before routine NHS practice can be systematically changed. When reducing SIB duration from 3-weeks to 1-week, adjustment to the total SIB dose (and dose delivered per Fr) is required to ensure that the 1-week SIB radiotherapy is as effective as the 3-week SIB without increasing side-effects; when local recurrence risk is very low the minimisation of side-effects for which all treated patients are at risk becomes paramount. Using radiobiological modelling based on clinical outcome data from FAST-Forward and IMPORT HIGH, it is possible to closely estimate the 1-week SIB dose equivalent to the 3-week IMPORT HIGH 48Gy/15Fr SIB dose. Given that the total boost dose is higher than the whole breast dose used in FAST-Forward (i.e. on a different part of the radiation dose-response curve for tumour and normal tissues), it is critical to obtain robust clinical safety and effectiveness data. The optimal RCT design thus again uses a 3-group trial (as used in START-A and FAST-Forward) whereby 2 test dose-levels estimate the lower and upper bounds of the biologically equivalent dose to that used in the control group. Such modelling hypothesises that a 1-week SIB of 30Gy or 31Gy in 5Fr (with 26Gy in 5Fr to the whole breast) is most likely to be equivalent to the 48Gy/15 Fr/3-week (with 40Gy in 15Fr to the whole breast) SOC; and the proposed trial design provides an efficient way to triangulate between the 1-week (5Fr) SIB doses to identify the 5Fr schedule most closely equivalent to 48Gy/15Fr if required.

Rationale for 30Gy and 31Gy in 5 fractions as choices of SIB dose: Using clinical results from our previous trials, we predict that both 30Gy and 31Gy in 5 treatments delivered over 1 week as a simultaneous integrated boost (SIB) will be similar in terms of cancer control with acceptable late breast tissue toxicity compared with our control of 48Gy SIB delivered in 15 treatments over 3 weeks. We hypothesise that there will be no difference in local control between 30Gy and 31Gy SIB given the shallowness of the dose-response curve, but we need to demonstrate prospectively that one or both schedules are non-inferior to 48Gy SIB in order to be able to change practice. If both test groups are non-inferior in terms of local breast cancer recurrence, we will select the test schedule that gives the least toxicity.

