From previous trials we have demonstrated that we are able to discriminate between the test groups in terms of late side-effects even though the total dose only differed by 1Gy. This is because data from our previous clinical trials suggest 30Gy and 31Gy SIB are biologically similar to 60Gy and 64Gy in 2Gy treatments respectively (assuming α/β of 2) for normal breast tissue toxicity, giving a biological dose difference of 4Gy i.e. a numerical difference of 1Gy in total dose translates to a biological difference of 4Gy for normal tissue toxicity given the steepness of the dose-response curve at this dose level, therefore, we expect to be able to show a difference in toxicity reports. The only circumstance under which the higher dose test schedule would be implemented in clinical practice would be if the lower dose test schedule is shown to be inferior to control arm for local tumour control, providing normal tissue toxicities are acceptable. NB The doses to non-breast organs-at-risk will be lower for both one-week test groups such that risks of longer-term side-effects in heart and lungs would be anticipated to be lower.

The table below shows EQuivalent total Doses in 2Gy fractions (EQD2) for the various 5W, 3W and 1W fractionation schedules tested/being tested in various trials for comparison.

Schedule	Alpha/beta (Gy)				
	Late NTE			Breast cancer	
	3.0	2.5	2.0	3.7	3.7 + *time
50Gy/25F (2.0)					
EQD2	50	50	50	50	50
40Gy/15F (2.67)					
EQD2	45	46	47	45	**+8=53
48Gy/15F (3.2)					
EQD2	60	61	62	58	+8=66
26Gy/5F (5.2)					
EQD2	43	44	47	41	+8=49
29Gy/5F (5.8)					
EQD2	51	54	57	48	+8=56
30Gy/5F (6.0)					
EQD2	54	57	60	51	+8=59
31Gy/5F (6.2)					
EQD2	57	60	64	54	+8=62
32Gy/5F (6.4)					
EQD2	60	63	67	57	+8=65

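### The health economic analysis pools both test doses unconditionally, so if the doses differ it will not estimate cost-effectiveness for the one schedule that would be adopted

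*Protocol*

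**What the plan says.** Protocol Appendix A3 sets the economic objective as "whether a 5-fraction radiotherapy boost to the breast (test groups 1 and 2) is cost effective relative to current UK practice", the comparator being the 15-fraction boost. Under Methods it fixes the comparison: "Data from the two test groups will be combined and compared with the control group consistent with previous HE analyses in FAST-Forward". The ICER rule that follows weighs one strategy against one other. The only reason given for pooling is precedent. The model takes in the cost of treating adverse events, further breast cancer events, and quality-adjusted survival from EQ-5D-5L.

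Section 1.1 (rationale for the SIB doses) describes two options of which one will be used:

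- On biology, at alpha/beta of 2: "30Gy and 31Gy SIB are biologically similar to 60Gy and 64Gy in 2Gy treatments respectively".
- On the expected result: "we expect to be able to show a difference in toxicity reports".
- On selection: "If both test groups are non-inferior in terms of local breast cancer recurrence, we will select the test schedule that gives the least toxicity".
- On the 31Gy schedule, the condition introduced by "The only circumstance under which the higher dose test schedule would be implemented in clinical practice" is that the lower dose proves inferior for local control and toxicity is acceptable.

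Section 10.1 makes pairwise comparison of each test group with control the default unless stated otherwise. The protocol pools the test groups in two other analyses and gives a substantive reason each time: near-identical mean lung dose for pneumonitis (section 10.1), and no expected difference for lymphopenia (section 18.1).

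**The concern.** The two test groups are competing options. The two-dose design exists partly to separate them on late effects, and those effects feed the economic model through adverse-event costs and EQ-5D-5L. A single pooled strategy averages the schedule that will be recommended with the one that will not.

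The case that matters most is the one in which 30Gy fails on local control and 31Gy is adopted. The pooled arm would then carry the recurrences of a schedule the trial had just rejected, and A3 has no provision for this. The kind of reason given for pooling in the pneumonitis and lymphopenia analyses is not offered here, and for late toxicity it would contradict section 1.1. At stake is whether the trial can say that the schedule it recommends is cost-effective, as distinct from 5-fraction treatment in general.

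**Working it through.** **1. Reproduce the protocol's dose gap.** Inputs are the schedules in section 1.1. Formula: EQD2 = D × (d + a/b) / (2 + a/b), where D is total dose and d is dose per fraction.

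| a/b (late effects) | 30Gy/5 | 31Gy/5 | Gap | Control 48Gy/15 |
|---|---|---|---|---|
| 2.0 | 60.00 | 63.55 | 3.55 | 62.40 |
| 2.5 | 56.67 | 59.93 | 3.27 | 60.80 |
| 3.0 | 54.00 | 57.04 | 3.04 | 59.52 |

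Rounded, these match the table in section 1.1 (60/64/62, 57/60/61 and 54/57/60). The stated 4Gy gap is the rounded figure at a/b = 2; at 2.5 and 3.0 the gap is 3Gy. The test doses lie on opposite sides of control only at a/b = 2. At the other two values both lie below it.

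**2. What equal pooling does.** Allocation is 1:1:1 with 1610 per group (section 5.1). For any mean outcome m, the pooled value is (m30 + m31)/2. Its distance from the adopted schedule's value is (m_other − m_adopted)/2, which is half the between-dose difference. If the difference is zero, the distance is zero.

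**3. Illustration on the net-benefit scale.** From section 1.1: saving £1,634 per person for 1-week treatment, and £15,000 per QALY. Assumed, and not in the documents: no QALY loss with 30Gy, a loss q with 31Gy, and the same saving for both. Net benefit against control is 1634 − 15000 × loss, and the pooled loss is q/2.

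| q (assumed) | 30Gy | 31Gy | Pooled |
|---|---|---|---|
| 0 | 1634 | 1634 | 1634 |
| 0.02 | 1634 | 1334 | 1484 |
| 0.05 | 1634 | 884 | 1259 |
| 0.10 | 1634 | 134 | 884 |
| 0.15 | 1634 | −616 | 509 |

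Taken alone, 31Gy reaches zero at q = 1634/15000 = 0.109. The pooled result reaches zero at q = 2 × 1634/15000 = 0.218. Between those values the pooled sign is wrong for 31Gy. Across the tabulated range it is never wrong for 30Gy, but its size is understated.

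**4. Precision given up by separating.** Assuming equal outcome variance in all groups, the standard error of a difference is proportional to √(1/n + 1/n) for one test group against control, and to √(1/n + 1/(2n)) for the pooled group. The ratio is √1.5/√2 = 0.866, so pooling saves about 13%.

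**The case against.** The strongest defence is that pooling fits the objective A3 sets itself, which is 5 fractions against 15. Dose selection is not left to the economics, because section 1.1 settles it by non-inferiority and then toxicity. The delivery saving is quoted once for 1-week treatment, so the doses can differ only through health effects and their costs. Section 10.4 defers the economic detail to a separate plan, which is not shown. All of this stands, and it is why the pooled comparison should stay in the analysis. It does not remove the point, because the protocol itself states the pooling rule and attaches no condition to it.

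A reader might infer that the pooled result describes no schedule that could be adopted. The documents do not support that: if the arms prove alike, the pooled result applies to both.

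A reader might also take 5-year recurrence of 3% and 5%, or induration of 11% and 16%, as the expected contrast between the doses. Those are control rates and the limits to be ruled out against control (section 10.1). Section 1.1 hypothesises no difference in local control between 30Gy and 31Gy, and no test-arm induration rate is given.

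Nor is a changed decision shown. The sign reversal in step 3 needs an assumed loss of 0.109 to 0.218 QALY with 31Gy, and no figure in the documents suggests one that large. If 30Gy is adopted and is the less toxic schedule, pooling understates its benefit, which is conservative.

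**Conclusion.** The point holds in a limited form. A3 fixes one pooled strategy on precedent alone, while section 1.1 expects the doses to differ in toxicity and admits only one to practice. The result will answer the 5- versus 15-fraction question. It will estimate cost-effectiveness of the adopted schedule only if the two doses turn out alike. Otherwise the estimate is shifted towards the schedule not adopted by half the between-dose difference, on the assumption of equal arm sizes. The size of that difference is unknown from the documents. This concerns a secondary endpoint and leaves design, sample size and data collection unaffected. It is worth correcting because the adopted schedule is the one on which a decision will be taken.

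**What to change.** In Appendix A3, Methods, replace the pooling sentence with a rule that costs and QALYs are estimated for Test Group 1 and Test Group 2 as separate strategies against control in the same decision model, each with probabilistic sensitivity analysis and its own acceptability curve. State that the decision result is the one for the schedule selected under the clinical rule in section 1.1, so that the economics does not become a second and possibly conflicting selection criterion. Keep the pooled 1-week versus 3-week comparison as a supporting analysis for the existing A3 objective.

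The cost is modest extra modelling on data already being collected. Each schedule's estimate is less precise: the standard error against control is about 15% larger than for the pooled group (1/0.866 = 1.155).
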